9.4 Monitoring

- 9.4.1 Routine labs (CBC, chemistry panel 14, LDH, magnesium, uric acid, phosphate) will be performed at baseline and on Day 1, 2, 8, 15, and 22 of cycle 1 and Day 1 of each cycle thereafter, end of therapy, and 1-year and 3-year after end of therapy. Myeloma tests include serum protein electrophoresis, serum immunofixation, beta-2 microglobulin, quantitative immunoglobulins and serum free light chains assay will be performed at baseline and Day 1 of each cycle, end of therapy, and 1-year and 3-year after end of therapy. Serum Lymphocyte subsets will be performed at baseline, Day 1 of cycle 4, and end of treatment. Routine labs, myeloma labs, and lymphocyte subsets can be performed 24 hrs in advance.
- 9.4.2 For patients with initial baseline 24-hr UPEP samples demonstrating ≥ 100 mg/24 hrs, patients will continue to have 24-hr UPEP samples day 1 of each cycle. Once 24-hr UPEP is < 100 mg/24 hrs, patient can have random UPEP with IFE until achieving negativity. If initial baseline 24-hr UPEP sample is IFE positive and/or < 100 mg/24, patients can have random UPEP samples with IFE until achieving negativity. Once random UPEP and IFE is negative, no further urine samples are needed (unless patient's disease is primarily measurable by 24 hr urines i.e. oligosecretory/hyposecretory)
- 9.4.3 Patients will have clinic visits with H&P or standard progress notes assessing for toxicity/side effects on Day 1, 8, and 15, of cycle 1 and Day 1 of each cycle thereafter 1-month after end of therapy, 1-year after end of therapy and 3-year after end of therapy. Treatment window for day 1 of start of each cycle is ± 7 days. Treatment window for intra-cycle carfilzomib doses is ± 2 days. Vital signs will be checked prior to administration of study drugs carfilzomib or daratumumab in all cycles.
- 9.4.4 At CR/sCR or end of therapy, routine labs (CBC, chemistry panel 14, LDH, magnesium, uric acid, phosphate), myeloma specific tests - serum protein electrophoresis, serum immunofixation, beta-2 microglobulin, quantitative immunoglobulins and serum free light chains assay, lymphocyte subsets, 24-hr urine sample for protein electrophoresis (UPEP) and immunofixation to assess for monoclonal protein in the urine (Bence-Jones proteinuria). A bone marrow biopsy will also be performed to assess the status of minimal residual disease by flow cytometry (Sample sent will be the first bone marrow "pull"). Patient will have clinic visit (relevant clinical laboratories and H&P) 1 month after completing combination therapy to undergo assessment of toxicities/adverse events.
- 9.4.5 Patients will have an echocardiogram (2-D or strain echo) performed at baseline and after completion of 6 cycles of therapy. Outside echocardiograms are permissible.
- 9.4.6 Patients will have FDG-PET-CT at baseline, end of therapy or upon suspicion of progressive disease as clinically indicated.

9.4.7 PFS and OS data will be collected for patients.

9.4.8 Stool sample collections are mandatory Stool samples will be collected prior to start of treatment during screening or before starting cycle 1, after cycle 1 (+14 days), and End of Protocol Therapy (EOS) +/- 14 days.

9.4.9 A medication log will be provided to patients to capture antibiotic use for patients collecting stool samples. Antibiotic use is not prohibited, but data will be captured for correlative purposes relating to analysis of stool microbiota.

9.5 After Protocol Therapy

9.5.1 Upon completion of protocol therapy, eligible patients will be encouraged to proceed onto maintenance therapy or high dose therapy with stem cell rescue under a separate treatment protocol or standard of care. If clinically indicated, patients may need additional alternative therapy.

9.5.2 After completion of protocol therapy, patients will remain on study for an additional 3 years for survival analysis, including annual MRD assessment when appropriate.

CONCOMITANT MEDICATIONS/MEASURES

TUMOR LYSIS SYNDROME

Hydration and Fluid Monitoring

- a) Oral hydration: For patients deemed at risk for TLS or dehydration, oral hydration may be considered (i.e., volume replete). Begin oral hydration equal to approximately 30 mL/kg/day (~6–8 cups of liquid per day), starting 48 hours prior to the planned first dose of carfilzomib. Compliance must be reviewed with the subject and documented by the site personnel prior to initiating treatment with carfilzomib; treatment is to be delayed or withheld if oral hydration is not deemed to be satisfactory.
- b) IV hydration: IV hydration will be administered per MSKCC institutional standards and can be adjusted at the clinical discretion of the investigator.

Management of Hepatitis B Virus Reactivation

Primary antiviral prophylaxis is permitted as per local standard of care. Per protocol, HBV DNA testing by PCR is mandatory for subjects at risk for HBV reactivation see Section 10.0.

For subjects who are diagnosed with HBV reactivation while on treatment, study treatment should be interrupted until the infection is adequately controlled. If the benefits outweigh the risks, study treatment may be resumed with concomitant antiviral prophylaxis as per local standard of care. Consult a liver disease specialist as clinically indicated.

Laboratory Monitoring

- 1) Appropriate basic metabolic panel chemistries, including creatinine for day 1 of each cycle and days 1, 8, and 15 of cycle 1, and complete blood counts (CBC) with platelet count should be obtained.
- 2) Subjects with laboratory abnormalities consistent with lysis of tumor cells, (e.g., serum creatinine \geq 50% increase, LDH \geq 2-fold increase, uric acid \geq 50% increase, phosphate \geq 50% increase, potassium \geq 30% increase, calcium \geq 20% decrease) prior to dosing should not receive the scheduled dose

Clinical Monitoring

- 1) Signs and symptoms indicative of TLS, such as fevers, chills/rigors, dyspnea, nausea, vomiting, muscle tetany, weakness, or cramping, seizures, and decreased urine output.

Management

- 1) If TLS occurs, cardiac rhythm, fluid, and serial laboratory monitoring should be instituted. Correct electrolyte abnormalities, monitor renal function and fluid balance, and administer therapeutic and supportive care, including dialysis, as clinically indicated.

Optional medication for high-risk TLS patients

- 1) Allopurinol is optional and will be prescribed at the Investigator's discretion. These subjects may receive allopurinol 300 mg PO BID (Cycle 1 Day -2, Day -1), continuing for 2 days after Cycle 1 Day 1 (total of 4 days), then reduce dose to 300 mg PO QD, continuing through Day 17 of Cycle 1. Allopurinol dose should be adjusted according to the package insert. The investigators do not anticipate the need for using rasburicase but it should be used if necessary according to indication and local guidelines.

BONE DISEASE/EXTRAMEDULLARY DISEASE

- 1) Radiation therapy: Subjects may receive limited local radiation for treatment of uncontrolled pain, cord compression, vertebral instability/impending fracture, etc.
- 2) Kyphoplasty/Vertebroplasty: Subjects may receive kyphoplasty/vertebroplasty for symptomatic vertebral compression fractures.
- 3) Bisphosphonate therapy: Approved bisphosphonate therapy (zoledronic acid or pamidronate) is allowed. Patients will be monitored for renal function and osteonecrosis of the jaw. Patients may require prior evaluation from dental specialist before instituting bisphosphonates.
- 4) Denosumab: Approved denosumab treatment is allowed.

HYPERCALCEMIA

Patients may receive treatment for hypercalcemia including hydration, bisphosphonates, furosemide, steroids, calcitonin, etc.

TRANSFUSIONS/GROWTH FACTORS

- 1) Subjects may receive RBC or platelet transfusions if clinically indicated.
- 2) Subjects may receive supportive care with erythropoietin or darbepoetin.
- 3) Colony-stimulating factors may be used if neutropenia occurs.
- 4) Growth factors and transfusions should not be administered prophylactically during cycle 1 unless clinically indicated.

ANTI-COAGULATION

Oral Aspirin 81 mg or 325 mg or suitable alternative anti-coagulation for thrombotic prophylaxis every day for the duration of their participation in the study.

HSV, VSV, PCP PROPHYLAXIS

Oral Valacyclovir of 500 mg daily or suitable alternative of Acyclovir throughout all cycles in which carfilzomib is given.

If CD4 count ≤ 200 /uL, PCP Prophylaxis with Bactrim/Pentamidine/Dapsone or suitable alternative should be considered by investigator unless there is a contraindication.

ANTI-EMETIC PROPHYLAXIS

Palonosetron 250 mg, or similar anti-emetics on day 1, 8, and 15 can be administered at the discretion of the treating physician.

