9.3 Non-Hematologic Toxicities Requiring Dosing Modifications

- 9.3.1 Any \geq Grade 3 toxicity require appropriate study drug to be held until resolved to Grade 1 or baseline (unless specified below in tables 9.4.4) prior to resuming therapy or initiating next cycle. Investigator will determine which drug will be held based on side effect profile and clinical judgment. If therapy has been held for more than 2 weeks due to non-hematologic toxicity, the patient will be removed from protocol therapy.

- 9.3.2 Protocol therapy will be withheld for patients who require treatment of Grade 3 infection. If therapy has been held for more than 3 weeks due to treating a grade 3 infection, the patient will be removed from protocol therapy.
- 9.3.3 For patients experiencing \geq grade 3 toxicity (unless specified below in tables 9.4.4), subsequent doses will be reduced at next dose level (according to the tables in section 9.2) if the adverse event was deemed to be attributed to study drugs. If the adverse event was deemed to be unrelated to study drugs, the patient may continue the full dose.
- 9.3.4 Electrolyte or metabolic abnormalities that are reversible with electrolyte replacement within 48 hours or $<$ grade 3 infections that can be controlled by appropriate therapy are exempt from holding treatment or dose modifications.

Lenalidomide Toxicities	Specific Dosing Modifications
Blistering Rash (Any Grade)	Discontinue lenalidomide and remove patient from therapy
Venous thrombosis/embolism	Hold lenalidomide and start therapeutic anticoagulation. Restart lenalidomide at investigator's discretion at current dose level.
Renal Dysfunction CrCl based on Cockcroft-Gault formula: $\text{CrCl} = (140 - \text{Age}) \times \text{Mass (in kilograms)} \times [0.85 \text{ if Female}] \div 72 \times \text{Serum Creatinine (in mg/dL)}$	
 CrCl 31-60 mL/min – Dose reduce lenalidomide to 10 mg daily from Days 1-21 CrCl ≤ 30 mL/min (not requiring dialysis) – Dose reduce Lenalidomide to 15 mg every 48 hours CrCl ≤ 30 mL/min (requiring dialysis) – Decrease Lenalidomide to 5 mg daily and on dialysis days give lenalidomide dose after dialysis.
Infection (\geq Grade 3)	
Hold therapy, treat underlying infection.
 
Remove patient from therapy if treatment of grade 3 infection persists for more than 3 weeks.

Carfilzomib Toxicities	Specific Dosing Modifications

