Allergic Reaction/Hypersensitivity	
 Grade 2: Hold carfilzomib until \leq Grade 1 and resume at full carfilzomib dose
Tumor Lysis Syndrome (≥ 3 of the following: $\geq 50\%$ increase in creatinine, uric acid, or phosphate; $\geq 30\%$ increase in potassium; $\geq 20\%$ decrease in calcium; or 2-fold increase in LDH)	Hold carfilzomib until all abnormalities in serum chemistries have resolved. Resume at full dose
Herpes zoster or simplex of any grade	Hold carfilzomib until lesions are dry. Resume at full dose
Neuropathy	Grade 2 treatment emergent neuropathy with pain: Hold carfilzomib until resolved to \leq Gr 1 without pain. Then restart at next dose level reduction.
Congestive Heart Failure	Patients with clinical symptoms and/or significant changes in EF ($>10\%$) will hold carfilzomib and repeat cardioechogram as clinically appropriate; if persisting/worsening clinical symptoms and/or significant changes in EF that is attributed to the therapy, the patient will be taken off the trial.
Hypertension (uncontrollable by medications, hypertension emergencies, or >3 episodes of hypertension urgencies)	
Hypertension uncontrollable by medications or >3 episodes of hypertension urgencies – hold carfilzomib and decrease to next dose level.
 
Hypertension emergency – stop therapy and go off protocol

Myocardial infarction	Any patient experiencing myocardial infarction will stop therapy and go off protocol
Posterior reversible encephalopathy syndrome (PRES)	If PRES is suspected, hold carfilzomib. Consider evaluation with neuroradiological imaging, specifically MRI, for onset of visual or neurological symptoms suggestive of PRES. If PRES is confirmed, permanently discontinue carfilzomib. If the diagnosis of PRES is excluded, carfilzomib administration may resume at the same dose, if clinically appropriate.

Carfilzomib Toxicities	Specific Dosing Modifications
Thrombotic microangiopathy (TMA)	If the diagnosis is suspected, hold carfilzomib and manage per standard of care including plasma exchange as clinically appropriate. If TMA is confirmed, permanently discontinue carfilzomib. If the diagnosis is excluded, carfilzomib can be restarted.

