Hepatitis B reactivation	Carriers of HBV who require treatment with Kyprolis should be closely monitored for signs and symptoms of active HBV infection throughout treatment. Any subject who becomes HBV DNA positive or develops reactivation of HBV should have carfilzomib treatment interrupted and receive appropriate anti-viral treatment as per a specialist in Hepatitis B.
Progressive Multifocal Leukoencephalopathy	Patients should be monitored for any new or worsening neurologic, cognitive or behavioral signs or symptoms that may be suggestive of PML as part of the differential diagnosis of CNS disorders. If PML is suspected, patients should be promptly referred to a specialist and appropriate diagnostic testing should be initiated. Discontinue Kyprolis if PML diagnosis is confirmed.

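### Hold rules for tumor lysis and hepatitis B reactivation differ between Section 9.3, the concomitant-measures text and Section 13.0, and no order of precedence is stated

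*Combined protocol and SAP*

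**What the plan says.** **Tumor lysis, Section 9.3, carfilzomib toxicity table.** The row is defined by at least "3 of the following": a rise of 50% or more in creatinine, uric acid or phosphate, a rise of 30% or more in potassium, a fall of 20% or more in calcium, or a doubling of LDH. The action is "Hold carfilzomib until all abnormalities in serum chemistries have resolved. Resume at full dose".

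**Tumor lysis, Concomitant Medications/Measures, Laboratory Monitoring, item 2** (placed after Section 9.5). The rule covers "Subjects with laboratory abnormalities consistent with lysis of tumor cells". The same six analytes and cut-offs follow as examples. Such patients "prior to dosing should not receive the scheduled dose".

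**Section 9.3.4.** Electrolyte or metabolic abnormalities that replacement reverses within 48 hours are exempt from holding. So are infections below grade 3 that appropriate therapy can control.

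**Hepatitis B, Section 9.3, carfilzomib toxicity table.** A patient who becomes HBV DNA positive or develops reactivation "should have carfilzomib treatment interrupted and receive appropriate anti-viral treatment".

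**Hepatitis B, Management of Hepatitis B Virus Reactivation** (also after Section 9.5). For diagnosed reactivation, "study treatment should be interrupted until the infection is adequately controlled". Treatment may then resume with antiviral prophylaxis if benefit outweighs risk.

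**Time limits.** Section 9.3.1: "If therapy has been held for more than 2 weeks due to non-hematologic toxicity, the patient will be removed from protocol therapy". Section 9.3.2 sets a limit of more than three weeks for treatment of a grade 3 infection. The infection row of the lenalidomide table and the off-therapy criteria in Section 13.0 repeat that limit.

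**The concern.** These are safety hold rules, and the protocol gives more than one answer on when they apply, which drug they cover and when treatment may restart. Two investigators could look at the same chemistry panel or HBV DNA result, act differently, and each cite the protocol. A monitor would then have no single standard against which to judge a hold, a resumption or a removal from therapy.

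The situations are within the protocol's own schedule. Section 9.4.1 has the relevant chemistries drawn repeatedly in cycle 1 and on Day 1 of later cycles. Section 6.2 admits patients with resolved hepatitis B who are PCR negative, and footnote b in Section 10.0 has their HBV DNA checked every 12 weeks on treatment. DNA positivity without a diagnosis of reactivation is therefore something the schedule can detect.

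**Working it through.** The plan gives no figure to reproduce on this point. The check sets the passages side by side and then counts where the two tumor lysis triggers part.

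**Tumor lysis**

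| Element | 9.3 carfilzomib table | Concomitant-measures text | 9.3.4 |
|---|---|---|---|
| Trigger | At least 3 listed changes | Changes consistent with lysis; same cut-offs as examples; no minimum number | Reversible with replacement within 48 hours |
| Drug | Carfilzomib | The scheduled dose, not named | Treatment in general |
| Action | Hold | Do not give | Exempt from hold |
| Resumption | When all have resolved | Not stated | Not applicable |

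Six analytes, each over its cut-off or not, give 2^6 = 64 patterns. Two points of wording are open. The table's list can be counted as 6 items, or as 4 if creatinine, uric acid and phosphate form one item. The concomitant text can mean any one change or, from its plural, at least two. Every change is taken as judged consistent with lysis, and 9.3.4 is left aside.

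- Table as 6 items, any one change: the rules differ for exactly one or two changes, C(6,1) + C(6,2) = 6 + 15 = 21 patterns.
- Table as 6 items, at least two changes: C(6,2) = 15 patterns.
- Table as 4 items: the table is met in 7 × 4 = 28 patterns (the combined item present in 7 of its 8 patterns, with at least two of the other three) plus 1 (combined item absent, other three all present), so 29.
  - Any one change: the concomitant text is met in 64 − 1 = 63 patterns, and 63 − 29 = 34 differ.
  - At least two changes: it is met in 64 − 1 − 6 = 57 patterns, and 57 − 29 = 28 differ.

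In every differing pattern the concomitant text withholds and the table's hold is not triggered; none runs the other way. No reading tried brings the count to zero.

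**Hepatitis B**

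| Element | 9.3 carfilzomib table | Concomitant-measures text |
|---|---|---|
| Trigger | HBV DNA positive, or reactivation | Diagnosed reactivation |
| Drug | Carfilzomib | Study treatment |
| Resumption | Not stated | Once controlled, if benefit outweighs risk |
| Time limit | Not stated | Not stated |

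- DNA positive, reactivation not diagnosed: the table interrupts carfilzomib; the concomitant text has no instruction.
- Reactivation diagnosed: both interrupt carfilzomib; only the concomitant text extends the interruption to study treatment as a whole.
- Length of hold: the concomitant text has no limit. Section 9.3.1 gives two weeks if the event counts as non-hematologic toxicity; 9.3.2 and 13.0 give three weeks if it counts as a grade 3 infection. Section 9.3.4 would exempt a controllable infection below grade 3 from holding at all. Nothing says which applies to reactivation.

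**The case against.** The strongest reply is that the passages can be followed together. The table says what to do once tumor lysis, as it defines it, is present; the concomitant text is a pre-dose precaution. Withholding on suspicion and then applying the table's resumption rule breaks neither. For diagnosed reactivation, interrupting all study treatment likewise satisfies both sections. This stands so far as it goes: neither section orders a dose to be given, and a reader who infers that the table requires dosing with one or two changes is reading an instruction into silence. But the protocol does not say that the rules are cumulative, so a site that applies only the table has not plainly departed from it.

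The example list might also be meant as shorthand for the table's definition. That is possible, but the text does not say so or cross-refer. The unnamed scheduled dose may well be carfilzomib, since the hydration text in the same section is framed around carfilzomib. That would narrow the drug question without settling the count.

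Three stronger inferences fail:

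- A reader might infer that an isolated calcium fall after treated hypercalcemia forces a missed dose. The concomitant rule requires abnormalities consistent with lysis, and a fall explained by treatment need not qualify.
- A reader might infer that daratumumab, lenalidomide and dexamethasone continue through reactivation under the table. That table is headed for carfilzomib and does not address the others; the lenalidomide table also holds therapy for infection of grade 3 or higher.
- A reader might infer that the two-week limit removes a patient before resumption is possible. The three-week infection limit may apply instead, and no document gives the time needed to control reactivation.

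**Conclusion.** The inconsistency is real and should be corrected. The tumor lysis part is the firmer: identical cut-offs, a minimum of three changes in one place and no minimum in the other, and a difference under all four readings tried (15, 21, 28 or 34 of 64 patterns). The hepatitis B part is narrower: the differences lie in trigger, drugs covered, resumption and the time limit that governs the hold.

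The pattern counts show that the texts diverge; they say nothing about how often patients would be affected, and the documents give no frequency. They rest on the changes being judged consistent with lysis and on 9.3.4 not applying.

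A reader might also infer that the conflict threatens the MRD result through missed doses or removals. The documents give no figure to support that, and the two-stage design and its error rates do not depend on these rules. The consequence is for consistent safety conduct and auditability.

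**What to change.** Reconcile Sections 9.3.1, 9.3.2 and 9.3.4, the Section 9.3 toxicity tables, the two concomitant-measures passages and Section 13.0. One place should carry the rule, with a cross-reference from the others.

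- **Tumor lysis:** the same trigger and number of abnormalities, how the list is counted, the drug or drugs covered, the resumption condition, and whether the 9.3.4 exemption applies.
- **Hepatitis B:** the same trigger (DNA positivity, diagnosed reactivation, or both), the drug or drugs covered, the resumption condition, which time limit governs the hold, and whether 9.3.4 applies.

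Which rule stands is for the sponsor and its safety reviewers. The cost is a few sentences in an amendment. No new tests are needed, because the chemistries and HBV DNA are already scheduled, and the sample size and analysis do not change.

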10.0 EVALUATION DURING TREATMENT/INTERVENTION

Study	Pre-Treatment	Induction											Follow-up		
		Cycle 1 ⁱ								Cycles 2-8			End of Therapy	1 month after EOT ^{i,j}	1, 2, and 3 years after EOT ^{i,m}
		Day 1	Day 2	Day 8	Day 9	Day 15	Day 16	Day 22	Day 23	Day 1 ^{io}	After completing 4-8 cycles	CR/sCR reached			
Medical Record Review	x												x	x	x
H&P with blood pressure	x	x		x		x				x			x	x	x ^m
Echo + EKG	x										x ⁿ				
ECOG	x									x			x		
Informed Consent	x														
Viral Studies ^b	x									x ^b			x ^b	x ^b	x ^b
Register for RevAssist	x														
Routine Labs ^a	x	x	x	x		x		x		x	x ^a		x		x ^m
Lymphocyte subsets	x									x ^a (only C4D1)			x		
Myeloma tests ^{f,j}	x ^{f,j}									x ^{f,j}			x ^{f,j}		x ^m
Urine for UPEP and IFE ^j	x ^j									x ^j			x ^j		x ^m
Pregnancy Test ^c	x ^{c,d}	x ^d	x ^d	x ^e		x ^e		x ^e		x ^c				x ^e	
Research Blood/Urine	x		x	x		x		x		x		x	x		x ^m
Bone Marrow/Aspirate	x ^g											x ^h	x ^h		x ^m

FDG PET-CT ^k	x												x		
Daratumumab Type and Screen Immunotherapy	x														
Stool Sample collection	X ^o									X ^o			X ^o		
Adverse Events/Toxicity		x								x			x	x	
Daratumumab ^p		x		x		x		x		X ^p					
Carfilzomib ^p		x	x	x	x	x	x			X ^p					
Lenalidomide ^p			x	x	x	x	x	x	x	X ^p					
Dexamethasone ^p		x	x	x	x	x	x	x		X ^p					
Acetaminophen/ ^p Diphenhydramine															
Montelukast ^p		x		x		x		x							

- a. Routine tests include CBC, reticulocyte count, Chem 14, magnesium, phosphate, uric acid, eGFR determination and LDH. Reticulocyte count will only be performed at baseline. PT and PTT will only be performed at baseline. Peripheral blood lymphocyte subsets at baseline, C4D1, and end of therapy. Complete Blood Count (CBC) WITH Differential will be performed on days 8 and 15 during cycles 2-8.
- b. Viral studies include hepatitis B surface antigen (HBsAg), hepatitis B surface antibody (Anti-HBs), and hepatitis B core antibody (Anti-HBc) and Hep C antibody. If Hep C antibody positive, Hep C RNA PCR will be performed.
 - *HPV DNA testing (if applicable)*: For subjects with serologic evidence of resolved HBV infection (i.e., positive Anti-HBs or positive Anti-HBc) at Screening, HBV DNA testing by PCR must be performed locally. Treatment Phase: Q12W during treatment, at the End of Treatment Visit, and Q12W for up to 6 months after the last dose of study treatment. Refer to Section 8.0.
- c. Pregnancy tests (urine or serum) for females of childbearing potential. A female of childbearing potential (FCBP) is a sexually mature female who: 1) has not undergone a hysterectomy or bilateral oophorectomy; or 2) has not been naturally postmenopausal for at least 24 consecutive months (i.e., has had menses at any time in the preceding 24 consecutive months)
- d. Pregnancy tests (urine or serum) must occur within 10 – 14 days and again within 24 hours prior to prescribing lenalidomide for Cycle 1 (prescriptions must be filled within 7 days).
- e. FCBP with regular or no menstruation must have a pregnancy test (serum or urine) weekly for the first 28 days and then every 28 days while on therapy (including breaks in therapy); at discontinuation of lenalidomide and at Day 28 post the last dose of lenalidomide. Females with irregular menstruation must have a pregnancy test (serum or urine) weekly for the first 28 days and then every 14 days while on therapy (including breaks in therapy), at discontinuation of lenalidomide and at Day 14 and Day 28 post the last dose of lenalidomide (see Appendix A: Risks of Fetal Exposure, Pregnancy Testing Guidelines and Acceptable Birth Control Methods).
- f. Myeloma tests include serum protein electrophoresis, serum immunofixation, 24-hr urine electrophoresis, urine immunofixation, serum free light chains, quantitative immunoglobulins, beta-2 microglobulin and will be performed at baseline.
- g. Bone marrow aspiration and biopsy will be sent for histopathology, flow cytometry, FISH/cytogenetics, heavy/light chain immunoglobulin rearrangement. Aspirate lysate will also be sent for cell sorting into CD 138- and + fractions and whole bone marrow lysate for HOTB storage so

molecular profiling with GEP and DNA-based sequencing at baseline can be performed as correlative work. Patients who have completed 1 cycle of standard of care therapy who meet eligibility criteria and have an HOTB sample at MSK within 60 days of cycle 1 day 1, will not need an additional bone marrow biopsy or aspirate, unless clinically indicated.

- h. Bone marrow aspirate and biopsy can be performed +/- 21 days of intended cycle day or achievement of CR/sCR. Bone marrow aspirate and biopsy will be sent to evaluate for histopathology, flow cytometry (bone marrow immunophenotyping of plasma cells), heavy/light chain immunoglobulin rearrangement. Aspirate lysate will also be sent for cell sorting into CD 138- and + fractions and whole bone marrow lysate for HOTB storage so molecular profiling with GEP and DNA-based sequencing at baseline can be performed as correlative work. For patients, reaching CR/sCR MRD negative timepoint earlier where MRD negative status is confirmed at earlier bone marrow evaluation, bone marrow aspiration and biopsy at end of study will be as per standard of care. Otherwise, all other bone marrow biopsies are strongly encourage for all cohorts.
- i. After study therapy ends at the completion of 8 cycles or after 4 cycles in patients who have <PR, follow-up will be 1 month after study end date. Patients may be followed at more frequent time intervals, and thereafter if clinically indicated. Patients who have progressive disease while on therapy will be followed with restaging scans and laboratory tests as clinically indicated. At disease progression, marrow and FDG-PET/CT are optional but recommended.
- j. For patients with initial baseline 24-hr UPEP samples demonstrating ≥ 100 mg/24 hrs, patients will continue to have 24-hr UPEP samples day 1 of each cycle. Once 24-hr UPEP is < 100 mg/24 hrs, patient can have random UPEP with IFE until achieving negativity. If initial baseline 24-hr UPEP sample is IFE positive and/or < 100 mg/24, patients can have random UPEP samples with IFE until achieving negativity. Once random UPEP and IFE is negative, no further urine samples are needed (unless patient's disease is primarily measurable by 24 hr urines)
- k. FDG-PET scan will be performed on patients at baseline, end of therapy or upon suspicion of progressive disease as clinically indicated..
- l. Variations of +/- 7 days of scheduled visits are permitted (Treatment window for day 1 of start of each cycle is +/- 7 days. Treatment window for intra-cycle carfilzomib and/or daratumumab doses is +/- 2 days). Patients who have completed 1 cycle of standard of care therapy who meet eligibility criteria and have had a PET scan read at MSK within 60 days of cycle 1 day 1, will not need an additional PET scan read at MSK within 60 days of cycle 1 day 1, unless clinically indicated.
- m. After 1, 2 and 3-year from completing therapy (+/- 1 month window), PFS and OS data will be collected on all patients. Patients will have formal evaluation with H&P, clinical labs, myeloma labs and bone marrow evaluating for MRD status as per standard of care. PFS and OS data may be collected over the phone along with review of medical records. Survival, PFS, and time to next line of treatment data may be collected on subsequent protocols that patients have consented for (maintenance protocols/bio-banking or storage protocols).
- n. Patients will have an echocardiogram (2-D or strain) performed at baseline and after completion of 6 cycles of therapy. Outside echocardiograms are permissible
- o. Stool samples will be collected prior to start of treatment during screening or before starting cycle 1, after cycle 1 (+14 day permitted) and End of Study (EOS) +/-14 days A food frequency questionnaire will be administered to patients once either on study or in follow up.
- p. The treatment schedule for cycles 1-8 is as follows:

Cohort 1:

- Cycle 1 ONLY: Daratumumab 16 mg/kg days 1, 8, 15, and 22; Carfilzomib 20 mg/m² per dose, days 2 and 3; Carfilzomib 36 mg/m² per dose, days 8, 9, 15, and 16; Dexamethasone 20 mg/dose, days 1, 2, 8, 9, 15, 16 and 22; Lenalidomide 25 mg/day, days 2 – 21 every 28 days; Montelukast 10 mg (first 4 doses of Daratumumab)
- Cycle 2: Daratumumab 16 mg/kg days 1, 8, 15, and 22
- Cycles 3-6: Daratumumab 16 mg/kg days 1 and 15

- Cycles 7-8: Daratumumab 16 mg/kg day 1
- Cycles 2-8: Carfilzomib 36 mg/m² per dose, days 1, 2, 8, 9, 15, and 16
- Cycles 2-8: Lenalidomide 25 mg/day, days 1-21 every 28 days
- Cycles 2: Dexamethasone 20 mg/dose, days 1, 2, 8, 9, 15, 16 and 22
- Cycles 3-4: Dexamethasone 20 mg/dose, days 1, 2, 8, 9, 15 and 16
- Cycles 5- 8: Dexamethasone 10 mg/dose, days 1, 2, 8, 9, 15 and 16

Cohort 2:

- Cycle 1 ONLY: Daratumumab 16 mg/kg days 1, 8, 15, and 22; Carfilzomib 20 mg/m² per dose, day 2; Carfilzomib 56 mg/m² per dose, days 8 and 15; Dexamethasone 20 mg/dose, days 1,2, and 22, 40 mg/dose days 8 and 15; Lenalidomide 25 mg/day, days 2–21 every 28 days; Acetaminophen 650 mg; intravenous Diphenhydramine 25 mg. Montelukast 10 mg will be administered prior to the first 4 doses of Daratumumab.
- Cycle 2: Daratumumab 16 mg/kg days 1, 8, 15, and 22; Acetaminophen 650 mg; intravenous Diphenhydramine 25 mg.
- Cycles 3-6: Daratumumab 16 mg/kg days 1 and 15; Acetaminophen 650 mg; intravenous Diphenhydramine 25 mg.
- Cycles 7-8: Daratumumab 16 mg/kg day 1; Acetaminophen 650 mg; intravenous Diphenhydramine 25 mg.
- Cycles 2-8: Carfilzomib 56 mg/m² per dose, days 1, 8, and 15
- Cycles 2-8: Lenalidomide 25 mg/day, days 1-21 every 28 days
- Cycles 2: Dexamethasone 40 mg/dose, days 1, 8, and 15; 20 mg/dose day 22
- Cycles 3-4: Dexamethasone 40mg/dose, Days 1, 8 15
- Cycles 5-8: Dexamethasone 20mg/dose, Days 1, 8, 15
- After receiving 4 or more cycles, patients who are considered to be eligible for subsequent high dose therapy/autologous stem cell transplant (ASCT) will be recommended to undergo autologous stem cell harvesting for potential use in the future. For patients who choose to undergo stem cell harvest, the subsequent cycle may be delayed for up to 7 weeks.

Clinical and Correlative Studies - To create a bone marrow (clinical pathology, whole BM lysate, CD 138+ fractions and CD 138- fractions cell sorting with subsequent correlatives on both fractions), peripheral blood, and urine sample bank. These samples may be used to later to evaluate biological activity of daratumumab, carfilzomib, lenalidomide, and dexamethasone. Timepoints and potential analyses are listed below:

Bone Marrow

Sampling Time Points of Bone Marrow correlative studies

- a) Baseline
- b) CR/sCR during cycles 2-and up to 8
- c) End of therapy
- d) 1, 2 and 3 year timepoints after completing therapy (optional)

	Baseline	During Cycles 2-8 if reaches CR/sCR	End of study therapy	1,2, and 3 year timepoints after completing therapy
Pathology/IHC	x	x	x	x
Multiparametric Flow Cytometry	x	x	x	x
FISH/Cytogenetics	x			
Molecular Pathology for light or heavy chain immunoglobulin rearrangement	x	x	x	x
Storage (sorted and whole cell lysate)	x	x	x	x

*Patients undergoing MRD evaluation or End of study evaluation, the first pulled sample will be sent for Multiparametric flow cytometry

- Potential studies on the stored bone marrow samples may include but are not limited to the following:

Bone Marrow Aspirate/Biopsy

Pathology/Immunohistochemistry

Immunohistochemical staining will be assessed using immunohistochemistry markers such as CD 138, light chains, CD56 etc. Microenvironment interactions will also be assessed using various immunohistochemistry markers for osteoblasts, osteoclasts, stromal cells and proteasome components.

Minimal Residual Disease

Flow cytometry: Immunophenotyping of aberrant plasma cells by flow cytometry currently involves, but is not limited to, the use of the following reagents: CD138, CD19, CD45, CD38, and CD56.

Characteristic changes in immunophenotypically abnormal plasma cells (CD38 bright and/or CD138 positive) include but are not limited to decreased or absent CD19 and CD45, decreased CD38, increased CD56, decreased CD27, decreased CD81, increased CD117. For patients with non-evaluable samples at MRD assessment, patients can opt for repeat MRD assessment or continue to receive a total of 8 cycles of CRd. The first pulled bone marrow sample will be sent for multi-parametric flow cytometry as a priority. Samples will undergo MRD testing per MSK institutional practice, see section 12.0 for further methodology practice.

Molecular pathology: For MRD samples utilizing the NGS LymphoSIGHT™ (Adaptive, CA) platform, the InVivoScript NGS platform, immunoglobulin heavy and kappa chain variable, diversity, and joining gene segments from genomic DNA obtained from CD138+ bone marrow (BM) cell lysate or cell-free supernatant BM aspirate were amplified using universal primer sets as described elsewhere²¹. An MM clonotype was defined as an immunoglobulin rearrangement identified by NGS.

Mass spectrometry based proteomics for minimal residual disease assessment: Serial urine and serum samples will be analyzed to detect clonotypic peptides representing patient's monoclonal immunoglobulin heavy and light chains using high resolution mass-spectrometry-based proteomics.

FISH and cytogenetics

Interphase FISH/cytogenetics will be performed on patients enrolled in this protocol.

DNA-based target mutations

Bone marrow aspirate samples will be analyzed for somatic mutations by exome-sequencing of targeted genes using MSK *myTYPE* platform (or equivalent e.g. MSK Impact Heme). After therapy, perform if response is \leq PR or evidence of gross residual disease on SPEP/UPEP

Cell Sorting and Bone marrow cell lysate

Bone marrow aspirate storage samples will be sorted into CD 138 + and CD 138 – fractions and whole bone marrow cell lysate per HOTB SOP.

Research Blood/Serum and Urine

- a) One 7-8 mL serum tube will be collected at baseline, Day 2, Day 8, Day 15, and Day 22 of Cycle 1, Day 1 of every cycle during cycles 2-up to 8, during Cycles 2-8 if CR/sCR is achieved, at the end of therapy, and at any time point if the patient has progression of disease. One 7-8 mL CPT tube will be collected at baseline Day 1 of every cycle during cycles 2-8, if CR/sCR is achieved, at the end of therapy, and at any time point if the patient has progression of disease.
- b) Urine (random samples of 10 mL) will be collected into a standard urine collection cup and sent for analysis and storage at each of the above timepoints. Time points include: baseline, Day 2, Day 8, Day 15 and Day 22 of Cycle 1, Day 1 of every cycle during cycles 2-8, if CR/sCR is achieved, at the end of therapy, and at any time point if the patient has progression of disease.
- c) Peripheral blood and/or urine samples from patients will be analyzed for potential serum or urine biomarkers as well as drug concentrations, and describe the association with clinical outcomes if the results of the study indicate a clinical or translational rationale for analyzing the samples.

Stool

- a) Stool samples will be collected at baseline or prior to start of cycle 1, after cycle 1 end of cycle 8 or end of study. Stool should also be collected at time of complete response and at time of disease progression. Sample may also be collected at investigator's discretion at a time point that corresponds to onset of reported symptoms.
- b) Volume: 2-5 mL of stool should be collected using the provided stool collection kit.
- c) Sample requirements and handling: Date and approximate time of stool collection should be noted and logged with the requisition form and on the personalized label on the stool container. Stool should be collected within up to 24 hours of sample submission using instructions provided to patient, and kept refrigerated using cold packs provided with sample collection kit provided to patient, until sample can be delivered to the processing laboratory/delivery location denoted on the requisition form.

Stem cell mobilization

[figure not shown]
